### 3.3.2 Exclusion Criteria

1. *De novo* small cell carcinoma of the prostate.
2. Has participated in a study of an investigational product and received study treatment or used an investigational device other than those specified in the protocol within 2 weeks of C1D1.
3. Hypersensitivity to cetrelimab, apalutamide, or any of its excipients.
4. Has received prior radiotherapy within 2 weeks of C1D1. Participants must have recovered from all radiation-related toxicities, not require corticosteroids, and not have had radiation pneumonitis. A 1-week washout is permitted for palliative radiation ( $\leq$ 2 weeks of radiotherapy) to non-central nervous system (CNS) disease.
5. Receipt of prior cetrelimab or another immune checkpoint inhibitor targeting PD-1/PD-L1 and/or CTLA-4 (e.g. pembrolizumab, nivolumab, ipilimumab). Prior treatment with sipuleucel-T is allowed.
6. Has an active autoimmune disease that has required systemic treatment in the past 2 years (i.e., with use of disease modifying agents, corticosteroids or immunosuppressive drugs). Patients on low dose oral weekly methotrexate are allowed. Replacement therapy (e.g., thyroxine, insulin, or physiologic corticosteroid replacement therapy for adrenal or pituitary insufficiency) or treatment with drugs (e.g. methimazole, neomercazol, carbamazole, etc.) that function to decrease the generation of thyroid hormone by a hyper-functioning thyroid gland (e.g., in Graves' disease) is not considered a form of systemic treatment of an autoimmune disease.

7. Has received a live vaccine within 30 days prior to the first dose of study drug. Examples of live vaccines include, but are not limited to, the following: measles, mumps, rubella, varicella/zoster (chicken pox), yellow fever, rabies, Bacillus Calmette–Guérin (BCG), and typhoid vaccine. Seasonal influenza vaccines for injection are generally killed virus vaccines and are allowed; however, intranasal influenza vaccines (e.g., FluMist®) are live attenuated vaccines and are not allowed. COVID-19 vaccine is allowed.
8. Individuals with concurrent second malignancy requiring active treatment at study entry that could affect safety or efficacy endpoints. Non-melanoma skin cancer, non-muscle invasive bladder cancer, and other carcinomas-in-situ are allowable exceptions.
9. Cardiac condition as defined as one or more of the following:
  - a. Uncontrolled supraventricular arrhythmia or ventricular arrhythmia requiring treatment
  - b. NYHA congestive heart failure class III or IV
  - c. History of unstable angina, myocardial infarction, or cerebrovascular accident within 6 months prior to C1D1
  - d. Uncontrolled hypertension defined as SBP  $\geq$  160 mm Hg and/or DBP  $\geq$  100 mm Hg. Treatment and re-screening are permitted.
10. History of seizure or pre-disposing condition (e.g. brain metastases). Medications known to lower seizure threshold must be discontinued at least 4 weeks prior to C1D1.
11. Has a diagnosis of immunodeficiency or is receiving systemic steroid therapy at a prednisone equivalent dose of  $>$  10 mg daily or other form of immunosuppressive therapy within 7 days prior to first dose of study drug.
12. Human immunodeficiency virus (HIV)-infected individuals on effective anti-retroviral therapy with undetectable viral load within 6 months are eligible for this trial (screening not required in the absence of risk factors).
13. For participants with evidence of chronic hepatitis B virus (HBV) infection (positive HBsAg and/or HBcAb), the HBV viral load must be undetectable at the time of study enrollment (screening not required in the absence of risk factors).
14. Chronic active HCV infection defined as positive viral load (screening not required in the absence of risk factors).
15. Has a history of (non-infectious) pneumonitis that required steroids or has current pneumonitis.
16. Gastrointestinal disorder affecting absorption.
17. Has an active infection requiring intravenous (IV) antibiotics within 7 days prior to C1D1.
18. Use of a prohibited concomitant medication (see Appendix 4 and Section 6.5.1) within 7 days of C1D1. Medications known to lower seizure threshold must be discontinued at least 4 weeks prior to C1D1.
19. Major surgery within 28 days prior to C1D1. Minor procedures including biopsies, dental surgery, cataract surgery, or outpatient procedure are allowed.

20. Has a history or current evidence of any condition, therapy, or laboratory abnormality that might confound the results of the study, interfere with the subject's participation for the full duration of the study, or is not in the best interest of the subject to participate, in the opinion of the treating investigator.
21. Has known psychiatric or substance abuse disorders that would interfere with cooperation with the requirements of the trial.

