## 5 Treatment Plan

### 5.1 Dosage and Administration

Treatment will be administered on an outpatient basis.

The starting dose of apalutamide will be 240 mg daily for patients not on apalutamide prior to study enrollment. For patients on apalutamide during Screening will be permitted to continue dose prior to enrollment.

Cetrelimab will be given at the recommended phase 2 dose of 480 mg via IV on day 1 of every 28-day treatment cycle. C1D1 dose will be administered over a 60-minute infusion. In the absence of infusion-related reactions, subsequent infusions may be administered IV over 30 minutes, depending on the volume administered. Subjects should be carefully observed during cetrelimab infusions. Trained study staff at the clinic should be prepared to intervene in case of an IRR. Resources necessary for resuscitation (e.g., agents such as epinephrine and aerosolized bronchodilator, medical equipment such as oxygen tanks, tracheostomy equipment, and a defibrillator) must be available at the bedside. Attention to staffing should be considered if multiple subjects will be dosed at the same time. If an IRR develops, then the infusion should be temporarily interrupted or slowed down and the guidelines in Section 6 should be followed to manage the IRR.

For the first infusion, vital signs should be assessed before the start of the infusion, every 15 to 20 minutes during the infusion, at the end of infusion, and approximately 2 hours after the end of

infusion. After the completion of the first infusion the subject may be discharged if considered clinically stable and all other study procedures have been completed. During subsequent infusions of cetrelimab, vital signs should be assessed pre-dose, once during infusion, and at the end of infusion. Cetrelimab infusions will be prepared and administered as described in the Investigational Product Preparation Instructions (IPPI).

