## 5.2 Dose Modifications and Management of Toxicity

Dose interruptions for up to 28 days are allowed. For treatment interruptions lasting > 28 days, resumption of treatment is only allowed if patients are experiencing clinical benefit and only upon approval of Principal Investigator.

If one or more agent(s) is permanently discontinued due to AE, the patient may continue to receive the other medication(s) within regimen.

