### 5.2.1 Retreatment Criteria for Cetrelimab and Apalutamide

**Table 5.2 Retreatment Criteria**

Adverse Event	Requirements before each study agent administration
Absolute neutrophil count	$\geq 1.0 \times 10^9/L$
Platelet count	$\geq 50 \times 10^9/L$ with or without platelet transfusions and/or growth factors
Hemoglobin	$\geq 8.0 \text{ g/dL}$ with or without transfusion, growth factors, or both
Fasting glucose, if prompted by HbA1c	$\leq 250 \text{ mg/dL}$
Hyperthyroidism	Grade $\leq 2$
AST and ALT	$\leq 3 \times \text{ULN}$ ( $\leq 5 \times \text{ULN}$ for patients with liver metastases)
Total bilirubin	$\leq 1.5 \times \text{ULN}$
Rash	Grade $\leq 2$
Other clinically significant toxicity 	Recovery to Grade $\leq 1$ or baseline

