### 5.2.2 Dose Delay for Cetrelimab

Dose reduction of cetrelimab is not permitted. Treatment delay of cetrelimab is required until re-treatment criteria are met (Table 5.2) and for any of the following AEs:

- Grade 2 pneumonitis (recurrent Grade 2 or Grade  $\geq$  3 pneumonitis, cetrelimab must be permanently discontinued)
- Grade 2 or 3 diarrhea or colitis
- Grade 2 nephritis with creatinine  $>$  1.5 – 3 x ULN
- Grade 2 or 3 creatinine elevation
- Grade 2 elevation in AST or ALT except for patients with liver metastases at baseline, or total bilirubin 1.5 – 3 x ULN
- Grade 2 toxicity related to treatment with cetrelimab that is intolerable or persistent (lasts  $>$  28 days)
- Symptomatic endocrinopathies (hypothyroidism, hyperthyroidism, hypophysitis, adrenal insufficiency diabetes)
- Grade 3 rash
- Other Grade 3 treatment related toxicity assessed as related to cetrelimab

If a cetrelimab dose must be delayed by more than 2 weeks, administration should continue at the next planned dosing date and the dose will be considered a missed dose.

Study treatment with cetrelimab should be permanently discontinued for any of the following:

- The investigator believes that for treatment-emergent toxicity it is in the best interest of the subject to discontinue study treatment
- Grade 4 toxicities except for:
  - endocrinopathies that are controlled with replacement hormones
  - Grade 4 hematologic toxicities that resolve in less than 7 days may not result in study treatment discontinuation at the discretion of the treating physician.
- Grade 2 or 3 irAEs that persist despite treatment modifications or corticosteroid dosing cannot be reduced to  $\leq$  10 mg prednisone or equivalent per day within 12 weeks
- A treatment-related AE does not resolve to Grade  $\leq$  1 within 12 weeks of the last dose of study drug unless otherwise agreed to by the sponsor medical monitor and the investigator based on evidence of clinical benefit
- Any non-hematological treatment-related event occurs a second time at Grade  $\geq$  3 severity
- Grade  $\geq$  3 (or recurrent Grade 2) pneumonitis
- Grade  $\geq$  3 nephritis with creatinine  $\geq$  3xULN
- Grade  $\geq$  3 elevation of AST or ALT  $>$  5xULN or total bilirubin  $>$  3xULN
  - For subjects with baseline Grade 2 elevation of AST or ALT due to liver metastasis, only Grade  $\geq$  3 elevations that are  $\geq$  50% of baseline for  $\geq$  7 days will require discontinuation of study treatment

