### 5.2.3 Dose Modification for Apalutamide

Apalutamide dose reductions due to toxicities other than rash are described in the table immediately below. Management of rash, including dose reductions, is described in Section 5.4. Apalutamide dose may be reduced as follows: first dose-level reduction to 180 mg/day, second dose-level reduction to 120 mg/day. If further dose reduction is required, apalutamide should be discontinued.

Event	Clinically Significant Hematologic and Non-Hematologic AEs Deemed Related to Apalutamide
Grade 1 or 2	Dose delay up to 4 weeks or dose reduction at the discretion of the investigator.
Grade 3	Hold apalutamide until AE has improved to Grade $\leq 1$ or baseline and resume with a dose reduction. If apalutamide cannot be restarted within 4 weeks, it should be discontinued. Discontinue for Grade 3 toxicity that recurs after 2 dose reductions.
Grade 4	Permanently discontinue apalutamide.

Doses re-escalation back to the previous dose level may be permitted upon discretion of the Principal Investigator.

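### Section 5.2.3 has no seizure rule for apalutamide: after a related Grade 3 seizure that resolves, its table says to resume at a reduced dose

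*Combined protocol and SAP*

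**What the plan says.** **At entry.** Section 3.3.2, criterion 10, excludes patients on the ground "History of seizure or pre-disposing condition (e.g. brain metastases". Criteria 10 and 18 both require drugs that lower the seizure threshold to be stopped at least 4 weeks before Cycle 1 Day 1. Section 6.5.1 carries prohibitions in the exclusion criteria into the treatment period.

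**On treatment.** Section 5.2.3 handles every apalutamide-related toxicity except rash in one table, by grade:

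- Grade 1 or 2: delay of up to 4 weeks, or a reduction, as the investigator chooses.
- Grade 3: hold until the event has improved to Grade 1 or less "or baseline and resume with a dose reduction". Apalutamide stops if it cannot be restarted within 4 weeks. There is also a recurrence limit: "Discontinue for Grade 3 toxicity that recurs after 2 dose reductions".
- Grade 4: permanent stop.

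The dose steps are "first dose-level reduction to 180 mg/day, second dose-level reduction to 120 mg/day", after which a further reduction means stopping. The Principal Investigator may permit a return to the previous dose level. Patients already on apalutamide may enter below 240 mg, since Section 5.1 says: "For patients on apalutamide during Screening will be permitted to continue dose prior to enrollment".

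**General rules.** Section 3.5 ends treatment for an unacceptable adverse event, or when the investigator judges the participant unfit for more. Section 5.2 covers the other drug: "If one or more agent(s) is permanently discontinued due to AE, the patient may continue to receive the other medication(s) within regimen". Section 7.3.5 allows re-challenge for selected adverse events that led to a stop, if the investigator considers it safe and ethical.

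**The concern.** The entry rule and the on-study rule point in different directions. A man who has had a seizure cannot enrol. A man who has a related Grade 3 seizure after enrolling is, by the wording of the dose table, to be put back on apalutamide once he recovers. No row, footnote or cross-reference in Section 5.2.3 treats seizure differently from any other related Grade 3 event.

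What is at stake is the safety of an individual participant: re-exposure to a drug already judged related to his seizure. A site that follows the table exactly would be compliant in restarting.

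**Working it through.** The plan gives no figure on this point, so the check is a reading of the rules plus a count of permitted restarts.

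**1. Where seizure appears.** It is named in exclusion criteria 10 and 18, and reached indirectly by the carry-over in Section 6.5.1. Convulsions appear once more, in Section 7.3.3.2, as an example of an event that may be considered serious. None of these says what to do with apalutamide after a seizure on study.

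**2. Whether the restart condition can be met.** Section 5.2.3 requires improvement to Grade 1 or less, or to baseline. Table 5.2 sets the same recovery standard for "Other clinically significant toxicity". An eligible participant has no seizure history at baseline, so a seizure that has resolved satisfies both.

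**3. Number of restarts.** Assume that each seizure is related, is Grade 3 and resolves within 4 weeks. Assume also that there was no earlier reduction for another toxicity, no re-escalation and no stop under Section 3.5, and that a patient entering below 240 mg moves to the next lower listed level.

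- Entry at 240 mg: event 1, resume at 180 mg; event 2, resume at 120 mg; event 3, stop. Two restarts.
- Entry at 180 mg: event 1, resume at 120 mg; event 2, stop. One restart.
- Entry at 120 mg: event 1, stop. No restart.

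Re-escalation can change these counts. A patient entering at 180 mg could go 180, 120, back to 180, then 120 before a recurrence follows two reductions. That is two restarts after seizures instead of one.

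**4. Comparison with other events.** The protocol does write event-specific stops. Immune-mediated encephalitis ends cetrelimab (Section 5.2.2). Blistering or mucosal involvement stops dosing of both drugs at once (Section 5.4, footnote b). Neither rule reaches apalutamide after a seizure.

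**5. Interaction with cetrelimab.** The permanent-stop list in Section 5.2.2 includes "Any non-hematological treatment-related event occurs a second time at Grade" 3 or higher. If treatment-related there includes events related to apalutamide, which the text does not settle, a second related Grade 3 seizure would end cetrelimab while Section 5.2.3 resumes apalutamide at 120 mg.

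**6. Frequency.** Section 1.6 reports 6 discontinuations for adverse events among 27 patients on the combination: 3 rash + 1 hypersensitivity + 1 serum sickness + 1 asthenia = 6. None was a seizure. That section gives no seizure count and the documents give no rate elsewhere, so an expected number among 24 participants cannot be computed.

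**The case against.** **The general stops already cover this.** Section 5.2.3 operates alongside Section 3.5, and an investigator may call a seizure unacceptable and stop both drugs. This stands: the protocol does not force a restart, and a reader who infers that it does goes too far. But unacceptable is not defined, while the table gives a definite instruction to resume. The investigator has to set that instruction aside to act safely.

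**Re-challenge is restricted.** Section 7.3.5 covers selected events only and requires the investigator to find re-challenge safe and ethical. That is correct, and it is weaker than a general permission. It still leaves seizure open.

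**Oversight exists.** Serious events go to the manufacturer within 24 hours (Section 7.3.7) and to the Data and Safety Monitoring Committee, and Grade 3 to 5 events are reviewed monthly by the Site Committee (Appendix 2). These reviews would probably notice a Grade 3 seizure, but they do not change the dose rule.

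**The documents do not prove that a permanent stop at any grade is needed.** This is fair. They give no seizure rate for apalutamide and refer to the brochure and package insert for adverse event information. The case rests on the protocol's own exclusion, which applies formally only at entry, and on the low cost of the rule.

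**The wider reading.** A reader might infer the same gap for brain metastases, because Section 6.5.1 and Appendix 4 allow brain radiotherapy at the investigator's discretion without mentioning apalutamide. The documents do not support that. Section 7.1.4 counts new lesions outside bone, and an indication for radiotherapy on treatment, as progressive disease. Section 3.5 stops both drugs at radiographic progression or unequivocal clinical progression. The exception is optional continuation of clinically stable patients until progression is confirmed. What remains is a tension between the radiotherapy allowance and Section 7.1.4.

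**Conclusion.** The point holds for seizure. Section 5.2.3 tells sites to resume apalutamide at a reduced dose after a related Grade 3 seizure that resolves within 4 weeks, and leaves related Grade 1 or 2 seizures to discretion. The restart counts are base-case counts under the assumptions stated with them, with a maximum of two from 240 mg. Under the proposed rule the count is zero at every entry dose.

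This is a safeguard against a rare event and a matter of trial conduct. It has no bearing on sample size, type I error or power. A mandatory apalutamide stop for brain metastases or brain radiotherapy is not warranted, since the progression rules already make stopping the default.

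**What to change.** Make two changes by amendment.

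- Section 5.2.3, new table row: *Seizure of any grade deemed related (possibly, probably or definitely) to apalutamide: permanently discontinue apalutamide, no re-challenge; cetrelimab may continue per 5.2 and 5.2.2.* This keeps the table's test of relatedness and uses the attribution categories of Appendix 2.
- Section 7.3.5, added to the re-challenge sentence: *except apalutamide after a related seizure (see 5.2.3).*

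If the amendment is open anyway, the radiotherapy note in Section 6.5.1 and Appendix 4 could be reconciled with the radiotherapy item in the Section 7.1.4 definition of progressive disease. That is optional.

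The cost is wording in two places and, for an affected participant, loss of one of the two study drugs. Eligibility, visits, imaging and the analysis do not change.

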### **3.4 Inclusion of Women and Minorities**

#### **3.4.1 Eligibility of Women and Minorities**

Individuals of any race or ethnicity are eligible for this study. The inclusion of women is not appropriate for the trial design given this is a study of prostate cancer.

#### **3.4.2 Recruitment of Minority Groups**

The study recruitment strategy aims to achieve representation of minority groups that reflects the demographics of the affected population in the catchment area. In particular, this will include utilization of collaboration with Lazarex Foundation to help defray travel costs associated with clinical trial participation for patients with limited financial resources, utilization of a Redcap clinical trial tracker (ucsftrials.com), with outreach to community oncologists serving minority groups within the UCSF catchment region, engagement with the Office of Community Outreach and Engagement (COE) with the UCSF Cancer Center.

### **3.5 Criteria for Treatment Discontinuation**

In the absence of treatment delays due to AEs, treatment (both study drugs) may continue until first occurrence of one or more of the following:

- Radiographic PD by PCWG3/RECIST 1.1 criteria. If patients are clinically stable in the judgment of treating investigator, continuation of protocol therapy is allowed until progression is confirmed by repeat tumor assessment performed  $\geq 4$  weeks following first scan demonstrating progression.
- Unequivocal clinical progression
- Inter-current illness that prevents further administration of treatment;
- Unacceptable AE(s);
- Participant decides to withdraw from the study;
- Significant participant non-compliance with protocol;
- Receipt of non-protocol therapy
- General or specific changes in the participant's condition render the participant unacceptable for further treatment in the judgment of the investigator
- Study closure
- Completion of 2 years of protocol therapy.

Patients with PSA-only progression in the absence of radiographic or unequivocal progression should remain on study treatment per PCWG3 guidelines.

### **3.6 Criteria for Study Discontinuation**

Participants will have safety follow up assessment 30 (+/- 7 days) and 100 days (+/- 14 days) following End of Treatment.

Following completion of safety follow up visits, patients will subsequently be followed for overall survival every 90 days (+/- 30 days) until death, withdrawal of consent, or the end of the study, whichever occurs first.

### **3.7 Primary Completion**

The estimated primary completion is approximately 24 months after the study opens to accrual.

### **3.8 Study Completion**

The expected study completion date is approximately 78 months after the study opens to accrual.

## **4 Investigational Products**

### **4.1 Description, Supply and Storage of Investigational Products**

#### **4.1.1 Apalutamide**

##### Classification

Apalutamide is in a class of medications called androgen receptor inhibitors.

##### Mechanism of Action

The mechanism of action of apalutamide is through inhibition of the androgen receptor. Apalutamide prevents AR nuclear translocation and DNA binding to AREs.

Unlike bicalutamide, apalutamide shows no significant agonist properties in a model of CRPC (e.g., AR-over-expressing prostate cancer cells; LNCaP/AR cells). Gene transcription of PSA and TMPRSS2 is inhibited by apalutamide and results in concentration-dependent reduction of these protein levels in vitro. Apalutamide was also shown to reduce proliferation of CRPC cells as well as increase apoptosis in mouse models of prostate cancer. In addition, apalutamide has significant anti-tumor activity in murine tumor CRPC models, where apalutamide showed dose-dependent tumor growth inhibition and tumor regression over a dose range of 0.1 to 10 mg/kg/day, with effects that were superior to bicalutamide.

